5.2.3 Safety laboratory parameters

Safety laboratory parameters to be assessed are listed in [Table 5.2.3: 1](#). For the sampling time points please see the flow chart.

A central laboratory result will be used to confirm eGFR for eligibility; the respective reference ranges will be provided in the ISF.

To ensure sufficient hydration, patients should be strongly encouraged to come not fasted to their study visits.

Instructions regarding sample collection, sample handling/ processing and sample shipping are provided in the Laboratory Manual in the ISF. Where samples are collected by the patient directly, appropriate instructions in lay language will be provided.

The central laboratory will provide reports to the investigator. It is the responsibility of the investigator to evaluate the laboratory reports. Clinically relevant abnormal findings as judged by the investigator will be reported as adverse events (please refer to [section 5.2.6](#)).

Lab tests may need to be repeated in case of required medical follow-up due to an adverse event or if a test was not successful due to incorrect specimen handling or storage.

To test the eGFR throughout the trial, the site will collect a small capillary blood volume from the patient with the Mitra[®] tool at visits indicated in the [flow chart](#). The Mitra[®] tool will also allow the patient to collect blood at home. Therefore, at home patients will need to collect one blood sample on their own (one Mitra[®] cartridge with two sampling tips) and ship them to the central lab or the site, if permitted by local legislation. Alternatively, the patient will need to take the specimens to the site directly.

The central laboratory will transfer the results of the analysis to the CRO.

The CKD-EPI Equation is used for reporting eGFR based on serum creatinine (see [appendix section 10.2](#)).

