6. INVESTIGATIONAL PLAN

6.1 VISIT SCHEDULE

All visits should be scheduled according to the [flow chart](#). Each visit date (with its window) is to be counted from Day 1 (Baseline visit). If any visit has to be rescheduled, subsequent visits should follow the original visit schedule.

All trial visits should be initiated preferentially in the morning. Patients should be instructed to take their FMV urine samples at home before attending the scheduled visit at the study site.

To ensure sufficient hydration, patients should be strongly encouraged to come not fasted to their study visits.

Unscheduled visits will be possible at the discretion of the investigator at any time in order to check the safety of the patient e.g following an interruption of 2 consecutive site visits. If the reason for removal of a patient from treatment is an adverse event or a clinically significant laboratory test result, the patient must be followed-up until complete resolution or stabilisation of the event or until follow-up is agreed adequate by the Investigator and sponsor.

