#### 4.11.2 Clinical Laboratory Evaluation

The analyses of laboratory data will be descriptive in nature. Analyses will be based on SI units and on standardized values for all parameters except urine albumin, urine protein, urine creatinine, UACR and PCR, which will be reported in the conventional units. Results from the central laboratory will be included in the reporting of this study for the following laboratory groups:

- Hematology
- Chemistry
- Urine Chemistry.

Laboratory parameters will be collected at the following visits, as per the CTP (for all parameters except eGFR collected at home via Mitra® micro sampling):

- Baseline (visit 2)
- Visit 5
- Visit 8
- Visit 11
- Visit 14 (end of study visit).

For eGFR collected at home via Mitra® micro sampling, these will additionally be collected at visits 3, 4, 6, 7, 9, 10, 12, 13 and will be collected bi-weekly at visits 2, 3 and 4.

For by-visit summaries, the last non-missing assessment (including repeat assessments) recorded at each visit will be summarized. In the case that there are multiple measurements taken on the same date and time, and these measurements are simultaneously the last non-missing assessment at a visit, then the mean of these measurements will be taken and this average will be used in the analysis. Unscheduled visits will not be included in the summary tables. Listings will present all visits, including unscheduled ones.

At each visit, laboratory measurements will be compared with the relevant laboratory reference ranges and categorized as abnormal (low/high) or normal:

- Low: below the lower limit of the laboratory reference range
- Normal: within the laboratory reference range (upper and lower limit included)

- High: above the upper limit of the laboratory reference range.

Descriptive summaries of the baseline, post-baseline and change from baseline in laboratory parameters will be presented by laboratory parameter and visit. Additionally, a summary of the number and percentage of patients with abnormal laboratory values will be presented by laboratory parameter and visit. Percentages will be based on the number of patients with a measurement at the visit (per parameter).

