#### 4.11.4 Physical Exam

Physical exam will be assessed at visits 2 (baseline), 5, 8, 11, and 14 (end of study). Physical exam findings are recorded per the eCRF as:

- Normal
- Abnormal – Clinically Significant
- Abnormal – Not Clinically Significant.

A shift table of the baseline to worst post-baseline physical exam finding by body system will be presented. The number and percentage of patients will be presented for each shift combination, and percentages will be based on the total number of patients with each physical exam result at baseline.

All assessments, including unscheduled and repeat assessments, will be considered in the shift table and will be included in the listing.

A by-patient listing of physical exam results will also be presented, including the patient identifier, patient population, visit, study day of finding, indication of whether exam was performed and reason examination not performed (if applicable), body system, physical exam result, additional details recorded on the eCRF for abnormal clinically significant results along with the corresponding AE number and medical history number.

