#### 4.13 Changes in the Conduct of the Study or Planned Analysis

The presentation of eGFR slope categories in this SAP differs from that of the protocol (e.g. the protocol specifies eGFR slope category ‘<1’ but this SAP specifies ‘>-1’) because the wording in this SAP reflects the value of the eGFR slope coming directly from the statistical mixed model, whereas the protocol refers to the eGFR decline rate that is equal to the negative value of the eGFR slope coming from the statistical model.

For the primary analysis, an additional eGFR slope category ‘> -1’ for the shift table will be presented in order to assess homogeneity of eGFR slopes for patients with an eGFR slope of  $> -1$ . The analysis specified in the CTP will be modified to a shift table of patients with categories of eGFR slopes of  $> -1$ ,  $> -3$  to  $-1$  and  $\leq -3$  mL/min/1.73m^2/year in each of the retrospective and prospective phases.

Summaries of clinically relevant laboratory abnormalities will not be performed as per the CTP due to a lack of available data.

As detailed in section 3.1.1.1, this study was terminated in July 2022.

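### The by-visit laboratory abnormality table misses abnormal results followed by a normal same-visit repeat or seen only at an unscheduled visit

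*SAP*

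**What the plan says.** SAP 4.11.2 sets two rules for the laboratory tables. For by-visit summaries, "the last non-missing assessment (including repeat assessments) recorded at each visit will be summarized". Separately, "Unscheduled visits will not be included in the summary tables". The abnormality display is of this kind: "a summary of the number and percentage of patients with abnormal laboratory values will be presented by laboratory parameter and visit". Listings are wider: "Listings will present all visits, including unscheduled ones", and every out-of-range result in them is flagged as low or high.

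The protocol explains how repeats and extra visits arise. In 5.2.3, "Lab tests may need to be repeated in case of required medical follow-up due to an adverse event"; the other reason given there is a test that failed because the specimen was mishandled or badly stored. In 6.1, "Unscheduled visits will be possible at the discretion of the investigator at any time in order to check the safety of the patient".

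Protocol 7.2.5 commits to summarising results outside the reference range and results classed as clinically relevant. It states no rule for repeats or unscheduled visits. SAP 4.13 withdraws the second part: "Summaries of clinically relevant laboratory abnormalities will not be performed as per the CTP due to a lack of available data".

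For the physical examination, SAP 4.11.4 tabulates baseline against the worst post-baseline finding: "All assessments, including unscheduled and repeat assessments, will be considered in the shift table".

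**The concern.** A reader of the safety section will want to know how many patients had an abnormal value of a given parameter after baseline. The only laboratory abnormality table in the available text reports status at each scheduled visit, after repeats have replaced earlier values. It cannot answer that question. Some out-of-range results that protocol 7.2.5 says will be summarised can then appear only as flagged lines in a listing, without a count or a denominator.

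The adverse event tables do not fill the gap. Protocol 5.2.3 asks for abnormal findings judged clinically relevant to be reported as adverse events. However, protocol 5.2.6.2 collects only events associated with a trial procedure, and SAP 4.11.1 analyses only those. An abnormal potassium unrelated to sampling would not be expected there.

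**Working it through.** The plan states no figure on this point, so the check is to apply its rules to every possible pattern of results.

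**Inputs.** The SAP rule (4.11.2) uses the last value at the scheduled visit and ignores unscheduled visits. The comparator counts a patient if any result is abnormal, with repeats and unscheduled visits included.

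**Patterns.** The first scheduled result is abnormal or normal (2). The same-visit repeat is absent, abnormal or normal (3). The unscheduled result is absent, abnormal or normal (3). That gives 2 × 3 × 3 = 18.

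| First scheduled result | Same-visit repeat | Unscheduled result | Patterns | Counted by SAP table | Any abnormal value |
|---|---|---|---|---|---|
| Abnormal | None | Any of the three | 3 | Yes | Yes |
| Abnormal | Abnormal | Any of the three | 3 | Yes | Yes |
| Abnormal | Normal | Any of the three | 3 | **No** | Yes |
| Normal | Abnormal | Any of the three | 3 | Yes | Yes |
| Normal | None or normal | Abnormal | 2 | **No** | Yes |
| Normal | None or normal | None or normal | 4 | No | No |

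**Result.** The SAP table counts 3 + 3 + 3 = 9 patterns and the comparator counts 9 + 3 + 2 = 14. The difference is 14 − 9 = 5 patterns: three where a normal same-visit repeat overrides an abnormal first result, and two where the abnormality is seen only at an unscheduled visit. These are counts of logical patterns, not of patients, and say nothing about frequency.

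**Direction.** If the last value is abnormal, some value is abnormal. The SAP count therefore never exceeds the any-abnormal count, and as a measure of patients ever abnormal it can only be too low. As a measure of status at the visit it need not be biased: the fourth row shows the last-value rule adding a patient whose first result was normal.

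**Rechecks at unscheduled visits.** The first row covers an abnormal scheduled result rechecked only at an unscheduled visit. The recheck is left out and the original abnormal value stays in the table, whatever the recheck shows.

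**Size.** The share of abnormal scheduled results lost to normal same-visit repeats is r × n, where r is the share repeated under the same visit and n is the share of those repeats that are normal. The documents give neither r nor n, nor the rate of abnormalities found only at unscheduled visits. The undercount is zero if neither situation occurs and otherwise cannot be computed.

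**The case against.** The strongest reply is that the by-visit table does what it claims: it reports status at a scheduled visit, and every out-of-range value is still flagged in listings that include unscheduled visits. For a failed specimen the later value is the right one to use. The trial gives no drug, compares no treatments and analyses safety descriptively. All of this stands, and it keeps the point minor. It does not supply a count of the missed results.

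Several stronger readings are tempting, and the documents do not support them:

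- *Any abnormal result that prompts a recheck vanishes from the tables.* It is lost only if the repeat is normal and is recorded under the same visit. The documents do not say how repeats are filed. Central-laboratory reporting (protocol 5.2.3) makes a later draw plausible, possibly at an unscheduled visit, and then the original value stays counted.
- *The dropped values are systematically those that led to action.* Protocol 5.2.3 ties repeats to adverse event follow-up or failed tests, not to an abnormal value as such.
- *Vital signs have the same defect.* SAP 4.11.3 also uses the latest value and leaves out unscheduled visits. But it plans only summary statistics and change from baseline, with no abnormality count and no normal limits.
- *The SAP contradicts itself by treating physical examination differently.* A three-level finding shown as a shift and a continuous value shown by visit are different displays. Section 4.11.4 is a useful precedent, not evidence of an error.
- *The withdrawn summaries of clinically relevant abnormalities would have caught these values.* Nothing says that they would have used repeats or unscheduled visits.

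**Conclusion.** The point holds in a limited form. The laboratory abnormality table can understate how many patients had any abnormal value, through two routes only: a normal repeat under the same visit, and an abnormality seen only at an unscheduled visit. No other table in the available text counts those results, although protocol 7.2.5 says out-of-range values will be summarised.

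This rests on reading the last-value rule as governing the abnormality table, which follows because that table is presented by visit. It also assumes that no laboratory display is hidden in redacted text. Any percentage put on the undercount would be a product of assumed shares, so none is given. The primary outcome is unaffected: it rests on eGFR slopes, and SAP 4.10.2 considers measurements from unscheduled visits when estimating the prospective slope. This is a minor improvement to safety reporting.

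**What to change.** Keep the by-visit tables in SAP 4.11.2 as they are. For laboratory parameters only, add one of these:

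- a shift table from baseline to the worst post-baseline category, shown separately for low and high; or
- the number and percentage of patients with any abnormal post-baseline value, by parameter.

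Use all valid scheduled, repeat and unscheduled results. Exclude only results voided for specimen handling or storage, and state that exclusion. This is the worst-finding, all-assessments basis that 4.11.4 already uses for the physical examination.

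The cost is one extra table from data already destined for the listings. Reported abnormality rates may be slightly higher than in the by-visit tables, and a footnote should explain why the two displays differ.

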#### 4.11.3 Vital Signs

The following vital signs parameters will be assessed at visits 2 (baseline), 5, 8, 11, and 14 (end of study):

- Heart Rate (beats/min)
- Systolic Blood Pressure (mmHg)
- Diastolic Blood Pressure (mmHg).

If multiple measurements are taken at a single visit, then the latest of the measurements will be summarized. Unscheduled visits will not be included in the summary table, but will be included in the listing.

Summary statistics will be presented for each vital sign parameter and the change from baseline in each vital sign parameter by visit.

By-patient and visit listings of vital sign parameters will be presented, including patient identifier, patient population, age, sex, visit, measurement day, heart rate measurement, systolic blood pressure measurement, diastolic blood pressure measurement, and weight (collected at unscheduled visits and at baseline).

#### 4.11.4 Physical Exam

Physical exam will be assessed at visits 2 (baseline), 5, 8, 11, and 14 (end of study). Physical exam findings are recorded per the eCRF as:

- Normal
- Abnormal – Clinically Significant
- Abnormal – Not Clinically Significant.

A shift table of the baseline to worst post-baseline physical exam finding by body system will be presented. The number and percentage of patients will be presented for each shift combination, and percentages will be based on the total number of patients with each physical exam result at baseline.

All assessments, including unscheduled and repeat assessments, will be considered in the shift table and will be included in the listing.

A by-patient listing of physical exam results will also be presented, including the patient identifier, patient population, visit, study day of finding, indication of whether exam was performed and reason examination not performed (if applicable), body system, physical exam result, additional details recorded on the eCRF for abnormal clinically significant results along with the corresponding AE number and medical history number.

#### 4.12 Determination of Sample Size

The trial is initially planned to be conducted in a cohort of 600 patients, pending feasibility and enrolment period. To obtain a good representation of patients across eGFR slopes spectrum, 600 patients are planned to be enrolled. The goal is to achieve 400 fast progressors with an eGFR slope  $\leq -3$  ml/min/1.73m^2/year and 200 slow progressor patients with an eGFR slope between  $-3$  and  $-1$  ml/min/1.73m^2/year).

The sample size determination is not based on statistical considerations, but on feasibility, and there is no formal statistical hypothesis defined in the study. However, the sample size of 600 patients is considered adequate to evaluate the homogeneity of the retro- and prospective slopes. If the true (unobserved) proportion of patients have an eGFR slope  $\leq -3$  mL/min/1.73m^2 based on retrospective data and in the prospective observed period is 70%, 600 patients will provide an estimate of the proportion of at least 67% with a probability of 95%.

On the other hand, if the true (unobserved) proportion of patients have an eGFR slope  $\leq -3$  mL/min/1.73m^2 based on retrospective data and in the prospective the observed period is 50%, 600 patients will provide an estimate of the proportion of at least 47% with a probability of 95%. Results based on these parameters would be considered less than success, i.e. that we are less likely to be able to suggest or “conclude” that the retrospective and prospective slopes are homogeneous.

This study was terminated in July 2022, due to decision of the sponsor (see section 3.1.1.1). All enrolled patients and their data available up to the termination will be used in any subsequent analyses.

#### 4.13 Changes in the Conduct of the Study or Planned Analysis

The presentation of eGFR slope categories in this SAP differs from that of the protocol (e.g. the protocol specifies eGFR slope category ‘<1’ but this SAP specifies ‘>-1’) because the wording in this SAP reflects the value of the eGFR slope coming directly from the statistical mixed model, whereas the protocol refers to the eGFR decline rate that is equal to the negative value of the eGFR slope coming from the statistical model.

For the primary analysis, an additional eGFR slope category ‘> -1’ for the shift table will be presented in order to assess homogeneity of eGFR slopes for patients with an eGFR slope of  $> -1$ . The analysis specified in the CTP will be modified to a shift table of patients with categories of eGFR slopes of  $> -1$ ,  $> -3$  to  $-1$  and  $\leq -3$  mL/min/1.73m^2/year in each of the retrospective and prospective phases.

Summaries of clinically relevant laboratory abnormalities will not be performed as per the CTP due to a lack of available data.

As detailed in section 3.1.1.1, this study was terminated in July 2022.

## 5 Appendix

### 5.1 GFR CKD-EPI Formula

Calculation Name		GFR CKD-EPI	
Formula	Units	Decimal Places	

Conventional:
 
Black or African American formulas:
 
Female with a serum creatinine value of <math>\leq 0.7</math> mg/dL  <math>166 \times (\text{Serum Creatinine (mg/dL)} / 0.7)^{-0.329} \times (0.993)^{\text{age}}</math>
 
Female with a serum creatinine value of <math>> 0.7</math> mg/dL  <math>166 \times (\text{Serum Creatinine (mg/dL)} / 0.7)^{-1.209} \times (0.993)^{\text{age}}</math>
 
Male with a serum creatinine value of <math>\leq 0.9</math> mg/dL  <math>163 \times (\text{Serum Creatinine (mg/dL)} / 0.9)^{-0.411} \times (0.993)^{\text{age}}</math>
 
Male with a serum creatinine value of <math>> 0.9</math> mg/dL  <math>163 \times (\text{Serum Creatinine (mg/dL)} / 0.9)^{-1.209} \times (0.993)^{\text{age}}</math>
 
White, American Indian, Alaska Native, Asian, Native Hawaiian, Other Pacific Islander, Other formulas:
 
Female with a serum creatinine value of <math>\leq 0.7</math> mg/dL  <math>144 \times (\text{Serum Creatinine (mg/dL)} / 0.7)^{-0.329} \times (0.993)^{\text{age}}</math>
 
Female with a serum creatinine value of <math>> 0.7</math> mg/dL  <math>144 \times (\text{Serum Creatinine (mg/dL)} / 0.7)^{-1.209} \times (0.993)^{\text{age}}</math>
 
Male with a serum creatinine value of <math>\leq 0.9</math> mg/dL  <math>141 \times (\text{Serum Creatinine (mg/dL)} / 0.9)^{-0.411} \times (0.993)^{\text{age}}</math>
 
Male with a serum creatinine value of <math>> 0.9</math> mg/dL  <math>141 \times (\text{Serum Creatinine (mg/dL)} / 0.9)^{-1.209} \times (0.993)^{\text{age}}</math>
 
Creatinine in mg/dL is rounded to 2 decimal places prior to applying the formula.
	mL/min/ 1.73m 	0	

SI:
 
Serum creatinine in <math>\mu\text{mol/L}</math> will be rounded to zero decimal place and converted to mg/dL by multiplying by 0.01131. This creatinine value in mg/dL will be rounded to 2 decimal places. This creatinine result will be used in the GFR Conventional formulas listed above.
	mL/min/ 1.73m 	0	
Limitations/Special Notes:	Age is truncated to a whole number prior to performing the calculation.		

Note that if a patient selects multiple races on the eCRF, the CKD-EPI formula for ‘Other’, should be applied.

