10.2 GFR CKD-EPI FORMULA

Calculation Name	GFR CKD-EPI	
Formula	Units	Decimal Places

Conventional:
 
Black or African American formulas:
 
Female with a serum creatinine value of ≤ 0.7 mg/dL $166 \times (\text{Serum Creatinine (mg/dL)} / 0.7)^{-0.329} \times (0.993)^{\text{age}}$
 
Female with a serum creatinine value of > 0.7 mg/dL $166 \times (\text{Serum Creatinine (mg/dL)} / 0.7)^{-1.209} \times (0.993)^{\text{age}}$
 
Male with a serum creatinine value of ≤ 0.9 mg/dL $163 \times (\text{Serum Creatinine (mg/dL)} / 0.9)^{-0.411} \times (0.993)^{\text{age}}$
 
Male with a serum creatinine value of > 0.9 mg/dL $163 \times (\text{Serum Creatinine (mg/dL)} / 0.9)^{-1.209} \times (0.993)^{\text{age}}$
 
White, American Indian, Alaska Native, Asian, Native Hawaiian, Other Pacific Islander, Other formulas:
 
Female with a serum creatinine value of ≤ 0.7 mg/dL $144 \times (\text{Serum Creatinine (mg/dL)} / 0.7)^{-0.329} \times (0.993)^{\text{age}}$
 
Female with a serum creatinine value of > 0.7 mg/dL $144 \times (\text{Serum Creatinine (mg/dL)} / 0.7)^{-1.209} \times (0.993)^{\text{age}}$
 
Male with a serum creatinine value of ≤ 0.9 mg/dL $141 \times (\text{Serum Creatinine (mg/dL)} / 0.9)^{-0.411} \times (0.993)^{\text{age}}$
 
Male with a serum creatinine value of > 0.9 mg/dL $141 \times (\text{Serum Creatinine (mg/dL)} / 0.9)^{-1.209} \times (0.993)^{\text{age}}$
 
Creatinine in mg/dL is rounded to 2 decimal places prior to applying the formula.
	mL/min/ 1.73m ²	0

SI:
 
Serum creatinine in $\mu\text{mol/L}$ will be rounded to zero decimal place and converted to mg/dL by multiplying by 0.01131. This creatinine value in mg/dL will be rounded to 2 decimal places. This creatinine result will be used in the GFR Conventional formulas listed above.
	mL/min/ 1.73m ²	0
Limitations/Special Notes:	Age is truncated to a whole number prior to performing the calculation.	

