#### 4.10.1.3 Calculation of eGFR from Serum Creatinine

Serum creatinine measurements will be converted into eGFR measurements according to the Chronic Kidney Disease Epidemiology Collaboration (CKD-EPI) formula, as given in section 5.1.

For retrospective data, if serum creatinine is unavailable but calculated eGFR values are available, then the calculated eGFR values will be used regardless of which formula was used to derive them. The formula used for the derivation will be collected on the eCRF and specified in the listings. If the formula is unknown, then it will be assumed that the CKD-EPI formula (see section 5.1) was used.

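### Slope-model eGFR is derived with a reporting formula that rounds creatinine, truncates age and lists eGFR to 0 decimals: small, largely avoidable random noise, with a one-sentence fix

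*SAP*

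**What the plan says.** SAP 4.10.1.3 says that serum creatinine measurements will be "converted into eGFR measurements according to the Chronic Kidney Disease Epidemiology Collaboration (CKD-EPI) formula, as given in section 5.1". SAP 5.1 attaches four resolution rules to that formula:

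- **SI units:** creatinine in µmol/L "will be rounded to zero decimal place and converted to mg/dL by multiplying by 0.01131".
- **mg/dL:** "Creatinine in mg/dL is rounded to 2 decimal places prior to applying the formula". On the SI path this is a second rounding.
- **Age:** "Age is truncated to a whole number prior to performing the calculation".
- **Result:** the column headed "Decimal Places" holds 0 for eGFR.

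Protocol 10.2 has the same rules, so the SAP follows the protocol here. For historical records that hold an eGFR but no creatinine, SAP 4.10.1.3 adds: "then the calculated eGFR values will be used regardless of which formula was used to derive them".

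SAP 4.10.2 then fits the random-slope model to the eGFR values and sorts patients by slope at cuts of -1 and -3 mL/min/1.73m²/year. Nothing there asks for unrounded eGFR, and neither document assesses the effect of the rounding.

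**The concern.** Whole-number eGFR and whole-year age suit a laboratory report. Here the primary quantity is a within-patient slope over 48 weeks, cut at declines of 1 and 3 mL/min/1.73m²/year. Rounding before the fit adds measurement error that can move a patient across a cut at random. It also slightly inflates the residual variance, which SAP 4.10.2 presents as a guide to slope reliability.

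Truncated age adds a further quirk. The formula's smooth age decline of 0.7% a year becomes one step at the birthday, or no step if no birthday falls between the first and last samples.

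The noise also differs between the phases being compared. It matters most for 48-week slopes or short histories and least for long histories. Carrying unrounded values avoids most of this at no cost.

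**Working it through.** **1. The plan's own figures.** The documents give no figure for rounding error or for within-patient variability. The only quantitative design statement (SAP 4.12) concerns N = 600 and has no bearing on rounding. By exact binomial, P(X ≥ 402 | 600, 0.70) = 0.949 and P(X ≥ 282 | 600, 0.50) = 0.935, against a stated 95% for each.

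**2. Error in one eGFR value.** Above the creatinine knot, eGFR is proportional to creatinine^-1.209 × 0.993^age. So:

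- Error from creatinine ≈ 1.209 × eGFR / creatinine × rounding error. The rounding error is at most 0.005 mg/dL on the mg/dL path. On the SI path it is at most 0.5 × 0.01131 + 0.005 = 0.0107 mg/dL. At eGFR 90 and creatinine 0.9, 0.01 mg/dL is worth 1.209 × 90 / 0.9 × 0.01 = 1.2.
- Error from truncated age: 0 to 0.7% too high.
- Error from integer eGFR: at most 0.5, with SD 1/√12 = 0.29.

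Passing values through the full SI chain (non-Black coefficients, both sexes, ages 40, 60 and 75) gives:

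| eGFR | Largest error | Error SD |
|---|---|---|
| 20 | 0.6-0.7 | about 0.3 |
| 30 | 0.7-0.8 | about 0.3 |
| 45 | 0.7-1.1 | about 0.3 |
| 60 | 0.9-1.2 | 0.3-0.5 |
| 75 | 0.8-1.4 | 0.3-0.4 |
| 90 | 1.1-2.4 | 0.4-1.0 |

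If creatinine arrives in mg/dL, the largest error is 0.6-1.7 over the whole range.

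**3. Error passed to a least-squares slope.** SD(slope) = SD(value) / √Sxx.

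- Venous, weeks 0, 12, 24, 36, 48: the spacing is 0.230 years, Sxx = 10 × 0.230² = 0.529 and √Sxx = 0.727. Integer eGFR alone gives 0.29 / 0.727 = 0.40 per year.
- Mitra, 16 values (every 2 weeks to week 12, then every 4): Sxx = 3733.75 / 52.18² = 1.371 and √Sxx = 1.171. Integer eGFR alone gives 0.25 per year.
- All roundings together: about 0.6 (venous), 0.4-0.6 (Mitra), 0.6 (4 retrospective values in 1 year), 0.2 (4 over 3 years), 0.1 (8 over 4 years).

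The age step at eGFR 60 is 0.007 × 60 = 0.42. On the venous schedule a step between mid-series visits contributes 0.42 × 3 × 0.230 / 0.529 = 0.55 per year, and no step contributes 0, in place of a smooth 0.42.

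**4. Against other noise.** Slope error SD without → with all SI roundings and truncated age, for assumed within-patient residual SDs (simulated eGFR 25-88):

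| Data | SD 1.5 | SD 3 | SD 5 |
|---|---|---|---|
| Venous, 5 values | 2.06 → 2.16 | 4.14 → 4.20 | 6.87 → 6.91 |
| Mitra, 16 values | 1.28 → 1.36 | 2.58 → 2.62 | 4.24 → 4.28 |
| Retrospective, 4 over 3 years | 0.67 → 0.70 | 1.34 → 1.35 | 2.24 → 2.25 |

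As variance, the venous row rises by (2.16/2.06)² - 1 = 10%, then 3% and 1%. A creatinine CV corresponds to a residual SD of about 1.209 × CV × eGFR, so at eGFR 50 CVs of 3% and 5% mean 1.8 and 3.0. Simulating the CVs directly (declines of 1-5/year, baseline eGFR bands 20-45, 45-60 and 60-90) adds 5-9% to the prospective slope variance at 3% and 2-3% at 5% on the SI path.

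**5. Slope categories.** In the CV simulation, 7-11% of patients change category with least squares on the SI path, and about 4-7% after approximate shrinkage. The moves go both ways. Measured against the true category, least-squares misclassification rises by 0.5-1.8 points at CV 3% (for example 40.2% to 42.0%) and by 0.1-1.0 points at CV 5%. In the shrunken-slope version of the residual-SD simulation, 2-8% change category. The net rise there is at most 0.8 points (venous, SD 1.5: 34.6% to 35.4%), and 0.3 or less at SD 3-5.

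**6. Which step matters.** Either creatinine rounding on its own changes misclassification by at most 0.2 points. Without integer eGFR, the SI creatinine roundings and truncated age together add only a few tenths of a point. Most of the net loss overall comes from integer eGFR.

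**The case against.** The case for leaving the plan alone has real force.

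- **The step that matters most is the least clearly prescribed.** Only a table column gives 0 decimals. No sentence says that the model uses integer eGFR, and a programmer might treat the column as a display format. This stands as an ambiguity. It is itself a reason to add a sentence, since two programmers could derive different slope categories.
- **Not all of the error is avoidable.** Protocol 8.3.1 lists year of birth only, historical eGFR may arrive already calculated, and the documents do not give the resolution at which laboratories report creatinine. If it arrives in whole µmol/L, the first rounding does nothing. This stands.
- **The Mitra figures rest on an assumption.** SAP 4.10.1.3 speaks of serum creatinine, and Mitra samples are capillary blood. Applying the section 5.1 chain to them is assumed here.
- **The study is exploratory and the net effect is small.** This stands, and it sets the importance of the point.

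A reader might infer something stronger: that each eGFR carries an error of 1-2.5, comparable to a yearly change of 1-3, so the shift table is compromised. The figures do not support that. It sets the worst case of one value against a change estimated from 4 to 16 or more values. Errors of 2-2.5 arise only near eGFR 90 on the SI path, and at eGFR 20-30 the maximum is below 1. A reader might also take the share of patients whose category changes as the share made wrong. With no other noise, rounding alone moves 8-22% of patients, but that situation does not occur in practice. With realistic noise many moves are into the correct category.

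**Conclusion.** The rules are explicit for creatinine and age and ambiguous for eGFR. They feed the slope models, and nothing in the text exempts those models. Their cost is a small loss of precision without material bias, at the size given in the working. Other within-patient variation dominates misclassification, and long retrospective histories are hardly affected.

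This rests on assumed creatinine CVs of 3-5% or residual SDs of 1.5-5, on the literal reading of the 0-decimal column, and on applying the chain to Mitra values. Shrinkage was approximated, and the SAP's autoregressive structure was not modelled. Early termination may shorten some prospective series. That enlarges rounding error and independent biological noise in the same proportion, so the relative share stays about the same. The point is a free improvement and does not put the primary shift table in doubt.

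**What to change.** Add to SAP 4.10.1.3 that eGFR for the slope models is computed from creatinine at its recorded precision, with no intermediate or final rounding, and, where birth data allow, with age at the sample date that is not truncated. Say whether Mitra creatinine goes through the same calculation. Keep the section 5.1 rounding for eligibility, listings and displays. Historical eGFR available only as a calculated value stays as recorded.

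The cost is a sentence or two in the SAP and one derived variable. No new data are needed.
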